Scalp involvement of 25% to < 50% at baseline	8.53 ± 6.41 NA	9.72 ± 11.3 NA
Scalp involvement of 50% to 100% at baseline	20.6 ± 25.9 NA	20.3 ± 35.7 NA

^a All subjects in Part B received INCB018424 1.5% cream BID.

**MEMORIAL SLOAN KETTERING CANCER CENTER
IRB PROTOCOL**

Study INCB 18424-206: This was a double-blind, active- and vehicle-controlled study in adults with AD. One hundred forty-seven subjects were randomized, and 132 subjects were treated with blinded study drug as of the cutoff date (28 JUN 2017). Blinded, unaudited data showed that 23 of the 132 treated subjects (17.4%) had a TEAE. The most frequently reported TEAE was nasopharyngitis, which occurred in 3 subjects (2.3%). One SAE of myocardial infarction was reported but was assessed by the investigator as not related to study drug; the subject had elevated cholesterol at baseline and was a long-time smoker, which likely contributed to the event. Of the 35 subjects who entered the open-label extension, 6 subjects (17.1%) had a TEAE. All TEAEs reported in the open-label extension occurred in 1 subject each. No SAEs occurred during the open-label extension[23]. No PK data were available as of the data cutoff date.

Topical ruxolitinib cream's limited adverse cutaneous events has been supported by clinical trials to date where cutaneous AEs have been infrequent and of similar frequency and severity as with vehicle control treatment. Adverse events reported with topical ruxolitinib were mostly related to application site, mostly mild to moderate (and judged to be unrelated to study medication), resolved, and did not require treatment discontinuation. Cutaneous AEs (dryness, pruritus, eczema, skin peeling) were seen with similar frequency in vehicle and topical ruxolitinib cream groups. Laboratory and ECG evaluations have not suggested any safety issues, specifically no instances of neutropenia, thrombocytopenia, or leukopenia. Based on vehicle controlled studies with topical ruxolitinib 1.5% cream, we do not expect significant systemic toxicities or local side effects from treatment with topical ruxolitinib 1.5% cream[23].

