All toxicities will be graded as per the Common Terminology Criteria for Adverse Events (CTCAE) version 5.0, and as applicable. All AEs (or clinically severe cutaneous adverse events, when CTCAE v5.0 grading not applicable) grade ≥ 2 with any attribution will be reported from initial application of topical intervention through the 56 day (and in those patients with a day 84) follow-up visit, and will be followed until the event resolves. If the AE does not stabilize/ resolve within a reasonable time (approximately 30 days), it should be followed until its clinical relevance and etiology can be reasonably explained[23].

Less common expected application-side adverse events include[23]:

- Dry skin
- Erythema
- Skin peeling
- Application site reactions irritation
- Skin burning
- Application site pruritus

General adverse events (unlikely or possibly to be related to topical ruxolitinib 1.5% cream), in both topical ruxolitinib 1.5% cream and vehicle arms of clinical trials include (in order of frequency)[23]:

- Upper respiratory tract infection
- Nasopharyngitis
- Sinusitis
- Influenza

MEMORIAL SLOAN KETTERING CANCER CENTER IRB PROTOCOL

- Back pain
- Electrocardiogram QT interval abnormal
- Diarrhea
- Gastroenteritis
- Headache
- Seasonal allergy
- Transient leukopenia
- Reticulocytosis
- Transient hypoesthesia

Based on a review of the extent of exposure, the incidence of AEs (including nonserious events, serious, severe, and/or life-threatening events, treatment-related events, and events that led to subject discontinuation), the clinical laboratory outcomes, the vital sign measurements, and the ECG findings, no safety signals or trends were observed.

All serious adverse events will be reported from initial application of study interventions through the day 56 ± 5 days safety visit, and the day 84 ± 5 days safety visit for those who repeat a topical ruxolitinib course, and will be followed until resolution.

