All patients will be evaluable for adverse events (toxicities) from the time of their first treatment with ruxolitinib until the end of the study visits or until they are lost to follow-up. All reported adverse events (AEs grade ≥ 2 with any attribution) during the study period through day 56 follow-up [and day 84 \pm 5 days for subjects who continue in the open-label extension] visit will be coded using Medical dictionary for regulatory activities (MedDRA) Version 20.0. For all adverse events, all treatment-emergent adverse events, all serious adverse events, and all adverse leading to discontinuation frequency distributions by system organ class and preferred term will be calculated and presented for each patient and each treatment side, when applicable. The safety of all patients enrolled in this study will be monitored throughout the study, and at safety visit 28 \pm 5 days following the last study dose. Safety monitoring will include history and physical examination with adverse event reporting. A follow-up safety evaluation will be done until end of study visit after discontinuing topical ruxolitinib cream treatment or withdrawal from the study for any reason. In addition, patients should notify the study staff of any problems that occur between visits by telephone and, if

**MEMORIAL SLOAN KETTERING CANCER CENTER
IRB PROTOCOL**

necessary, be evaluated by the Investigator or study staff at an unscheduled interim hospital visit.

Treatment adjustments: Patients who report or exhibit treatment-related AEs should have their treatment exposure reduced or discontinued. If no frequency of study drug application is tolerated for any of the patient's lesional skin, then the patient must be withdrawn from the study. Treatment interruptions for non-medical reasons are at times unavoidable and are permissible under this protocol but must be documented. However, every attempt should be made to avoid any non-medical treatment delays

- Grade 1 – 2: No change to study drug dose. Continue clinical monitoring.
- Grade 3 (with attribution possibly, probably, or definitely related): Hold study drug until AE improves to grade ≤2.
- Grade 4 (with attribution possibly, probably, or definitely related): Discontinue study drug.

Adverse Event Definitions

The following definitions of terms guided by the International Conference on Harmonization and the US Code of Federal Regulations apply to this section:

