17.0 PROTECTION OF HUMAN SUBJECTS

Prior to the enrollment of each patient, the risks, benefits and objectives of the study will be reviewed with the participant, including a discussion of the possible side effects. Patients reserve the right to withdraw participation from this study at any time.

Risks: It's unlikely that significant risks will be associated with the limited use of topical ruxolitinib 1.5% cream planned in this study.

Benefits: The early use of topical ruxolitinib 1.5% cream is hypothesized to reduce BSA of non-sclerotic and superficially sclerotic chronic cutaneous. This would serve as a novel topical therapy for management of non-sclerotic and superficially sclerotic chronic cutaneous GVHD and would improve patients' symptoms during treatment.

Possible toxicities/ adverse events. Local application-site side effects anticipated with ruxolitinib include dry skin, erythema, pruritus, skin peeling, and irritation. These adverse effects are not expected to necessitate treatment interruption. Systemic toxicities are rare, including upper respiratory tract infection and nasopharyngitis. Toxicities of topical ruxolitinib 1.5% cream are elaborated in section 11.0 of this protocol. The investigators will use a standardized form to assess irritation, pruritus, erythema and during the visits, as well as rare reactions that could be reported by the patient.

**MEMORIAL SLOAN KETTERING CANCER CENTER
IRB PROTOCOL**

Consent process: Participation in this protocol is voluntary. All patients will be required to sign a statement of informed consent, which must conform to MSKCC IRB guidelines.

Costs: Patients will not be charged for protocol related costs

Alternatives: There are no FDA-approved topical therapies for the treatment of non-sclerotic or superficially sclerotic chronic cutaneous GVHD; however, efficacy has been reported with topical corticosteroids.

Confidentiality: Every effort will be made to maintain patient confidentiality. Research and hospital records are confidential. Patients' names and any other identifying information will not be used in reports or publications resulting from this study. Other authorized agencies and appropriate personnel may review patient records as required.

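### The by-side safety tables are limited to grade 2 or higher, so they would leave out grade 1 application-site reactions

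*Combined protocol and SAP*

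**What the plan says.** The grade threshold appears twice in the combined protocol and SAP.

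- Section 11.0 states that events "grade ≥ 2 with any attribution will be reported from initial application of topical intervention". For skin events that CTCAE cannot grade, it extends reporting only to severe ones: "or clinically severe cutaneous adverse events, when CTCAE v5.0 grading not applicable".
- Section 14.0, Safety and Tolerability, names the events to be MedDRA-coded: "AEs grade ≥ 2 with any attribution". For these it plans that "frequency distributions by system organ class and preferred term will be calculated and presented for each patient and each treatment side, when applicable".

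On what is expected, Section 11.0 summarises earlier experience: "Adverse events reported with topical ruxolitinib were mostly related to application site, mostly mild to moderate". It also calls cutaneous events infrequent and similar to vehicle. Section 17.0 names dry skin, erythema, pruritus, peeling and irritation as anticipated local effects, does not expect them to interrupt treatment, and adds: "The investigators will use a standardized form to assess irritation, pruritus, erythema". Section 14.0 gives that form no analysis, and the appendix list in Section 20.0 does not include it.

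**The concern.** Each patient applies ruxolitinib to one side and vehicle to the other, so each patient is their own control for local reactions. That suits a by-side safety table well. If the table starts at grade 2, the mild part of the expected profile cannot appear in it. A mild reaction that occurred more often on one side would be invisible there, and an empty table could be misread as showing that no local reactions occurred. Section 11.0 reports that cutaneous events were about as frequent with vehicle as with ruxolitinib. A table starting at grade 2 could not check this for mild reactions in the present population.

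**Working it through.** The plan gives no figure on this point, so the main check is a reading of the rules side by side.

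1. *Is grade 1 excluded from the tables?* Section 14.0 goes on to speak of tabulating all adverse events, which could suggest all grades. That sentence follows the definition limited to grade 2 or higher, and only coded events can be arranged by system organ class and preferred term. The tables therefore inherit the threshold.
2. *Do ungradable skin reactions enter?* Only if clinically severe (Section 11.0).
3. *Is grade 1 tabulated anywhere else?* No section plans it. Section 16.0 records treatment-related toxic effects with no stated grade limit, Section 14.0 has grade 1 events monitored, and it promises individual listings and descriptive summaries of toxicity. None of these specifies a grade 1 table by side.
4. *Do other by-side measures cover it?* PRO-CTCAE is completed for each side and tested by subdomain with the Wilcoxon signed rank test, but it is the patient's report. In CAILS the dermatologist scores erythema, scaling and pruritus on each side from 0 to 8. Those items are summed with a body-surface-area grade, the day 28 analysis uses the ratio of total scores to baseline, and no item-level analysis is planned. Irritation and dryness are not CAILS items.

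*Can the loss be sized?* The nearest figure is in Section 11.0, from the vehicle-controlled psoriasis study: 30/199 = 15.1% of subjects had a treatment-related event, overall mild or moderate. Applied to this trial, 24 × 0.151 = 3.6 patients (binomial 2.5th to 97.5th percentiles, 1 to 7). That is not the quantity needed. The rate covers all organ classes and is pooled across treatment groups, so it is neither a local rate nor a per-side rate, and no grade 1 share is given.

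An illustration on assumptions alone shows how the threshold would act. Let p be the share of the 24 patients with any application-site event on a given side, and s the share of those whose events are grade 1 only. Expected patients in the table are 24p with all grades and 24p(1 − s) with the threshold. The chance that the side is empty is (1 − p)^24 and (1 − p(1 − s))^24 respectively.

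| p (assumed) | Expected, all grades | Expected, grade ≥2 (s = 0.5 / 0.7 / 0.9) | Empty side, all grades | Empty side, grade ≥2 (s = 0.5 / 0.7 / 0.9) |
|---|---|---|---|---|
| 0.10 | 2.4 | 1.2 / 0.72 / 0.24 | 8% | 29% / 48% / 79% |
| 0.15 | 3.6 | 1.8 / 1.1 / 0.36 | 2% | 15% / 33% / 70% |
| 0.25 | 6.0 | 3.0 / 1.8 / 0.6 | 0.1% | 4% / 15% / 55% |

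The proportion removed is simply s, which is assumed. The table shows the mechanism and does not estimate the loss.

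**The case against.** The strongest reply is that a grade threshold is an ordinary choice for a 24-patient pilot, that mild symptoms are captured by side through PRO-CTCAE and CAILS, and that grade 1 erythema or pruritus on lesional skin is hard to tell from GVHD. Much of this stands. It is why the point is minor and why any added table has to be read against the vehicle side. It does not supply an investigator-observed record of mild application-site reactions by side.

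A reader might also infer more than the documents support:

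- *That by-side tolerability is a stated objective.* Section 2.0 asks for safety and tolerability by examination and adverse event reporting, without mention of side. The split by side appears only in the Section 14.0 tables, where applicable.
- *That mainly mild reactions are expected, or that they will be common.* The wording is mild to moderate. Moderate reactions, if grade 2, would be counted. Section 11.0 also lists the local reactions as less common.
- *That grade 1 events will go unrecorded.* Section 16.0 has no grade limit. What is missing is a rule for tabulating them.
- *That about 3.6 patients' events would vanish.* For the reasons given in the check, the 15.1% does not measure this.

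**Conclusion.** The point holds as a limited gap in reporting. Two sections restrict reported and coded events to grade 2 or higher, or to clinically severe skin events where CTCAE does not apply, and nothing else in the plan tabulates grade 1 application-site reactions by side. The conclusion rests on reading the Section 14.0 tables as confined to the coded events, which is the natural reading. The size of the loss is unknown and cannot be derived from the documents. Efficacy analyses are not touched, so this is an optional, low-cost improvement.

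**What to change.** Keep the grade 2 threshold for general adverse events. For application-site reactions:

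- Record any grade, separately for each side, at the day 14 and day 28 CTCAE assessments already scheduled in Section 10.0, Table 1.
- Tabulate by treatment side for the blinded period only, ending at the day 28 visit. After that, ruxolitinib may go on both sides (Section 4.2) and the vehicle contrast is lost.
- Show grade 2 or higher as a subset, and give within-patient counts: ruxolitinib only, vehicle only, both.
- Do not rely on the Section 17.0 form alone. It names only irritation, pruritus and erythema, and no side or grade field is described. If it is kept, state whether it is completed for each side and how it will be summarised.

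The cost is modest extra data entry and one table. Because grade 1 erythema or pruritus on lesional skin may be GVHD itself, a footnote should say that the table is to be read as a contrast with the vehicle side and not as an absolute rate. The change concerns recording and reporting only.

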1.0 PROTOCOL SUMMARY AND/OR SCHEMA

Title: A Pilot, Prospective, Randomized, Double-Blinded, Vehicle- and Comparator-Controlled Trial on Safety and Efficacy of a Topical Inhibitor of Janus Kinase 1/2 (Ruxolitinib INCB018424 Phosphate 1.5% Cream) for Non-Sclerotic and Superficially Sclerotic Chronic Cutaneous Graft-Versus-Host Disease (GVHD).

Total Study Follow-up per patient: 56 days

Schema

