4.2 Intervention

Lesional areas will be chosen by the attending dermatologist. Lesional areas of the same corresponding size on the left and right hand sides of the participant will be evaluated, demarcated, imaged. In this study, participants will provide both treatment and vehicle control lesions. Eligible patients will be randomized to one of two treatment groups: Group 1 will be randomized to topical ruxolitinib BID to **left** side of face/body and topical moisturizer BID to **right** side of face/body; Group 2 will be randomized to topical ruxolitinib BID to **right** side of face/body and topical moisturizer BID to **left** side of face/body. Randomizing the treatment side is to maintain blinding of the physician. For example: if patients are all assigned to apply topical ruxolitinib to their right side and are showing clinical improvement on each patient's right side consistently, the physician will be aware that the right side is the treated side, possibly adding bias to the study. Variability in application side will also help to account for inter-patient variability in application with right- versus- left hand. Participants and their study doctor will be blinded from knowing which side of the face/body will be treated with the study cream, and which side of the face/body will be treated with the vehicle. For study purposes, Study Day 1 is defined as the first day of topical application. Patients will self-administer topical ruxolitinib and vehicle topically to affected rash area on directed side of face/body and record topical application on study diaries that will be provided by the study doctor or a member of the research team. On Study Day 28, end of treatment day, all patients will be eligible for the open label portion of the study. The attending will determine the patient's response, and if the patient wishes to continue, then they will be given the opportunity to use the topical ruxolitinib for an additional 28 days. If the patient wishes to continue then pharmacy will dispense open label ruxolitinib for the patient to apply to both sides of the body, not to exceed 20% total BSA. The PI, the Clinical Research Coordinator, and the patient will remain blinded to the initial treatment arm, but will become unblinded during the open label portion."

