16.0 DATA MANAGEMENT ISSUES

Data forms will be developed for recording all information pertinent to the observations and tests described in this protocol. All study data will be collected by an assigned data manager who will enter this information into MSK Medidata in a timely and accurate manner. All data and forms gathered for this study will be collected and stored in a secure location in facilities of the Dermatology Service. Regular meetings attended by the data manager and the Principal Investigators will be held to review study progress and to manage any difficulties encountered.

The data manager will collect toxicity and self-reported compliance data via patient's diaries and patient interviews. Adverse events, including all toxic effects related to treatment will be recorded individually according to toxicity date.

All clinical photographs will be maintained in digital format in a computerized archive (DermagraphixTM). This system labels each clinical photograph with study subject MRN, lesion number, and photograph date.

All patient data and questionnaires will be accessed on the Health Information System (HIS) and Mirror Dermagraphix database, which are password protected with user level access. All the data will be entered and maintained in MSK Medidata. During data analysis, de-identified data will be sent to investigators at Hackensack Medical Center for collaboration and manuscript preparation. All de-identified shared with Hackensack Medical Center investigators will be sent via MSK secure email.

The first interim data analysis will occur after the study has accrued 10 evaluable participants. Only the biostatistician and Dermtech personnel will be unblinded during the analysis.

The second interim data analysis will occur with the remaining 14 evaluable participants. Only the biostatistician and Dermtech personnel will be unblinded during the analysis.

Estimated time of accrual: 26 months
Accrual Rate: 1-4 patients per month
Time to complete study: 36 months

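### The by-side adverse-event table has no cut at day 28, although ruxolitinib is compared with vehicle only until then

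*Combined protocol and SAP*

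**What the plan says.** **Window.** Section 14.0, item 6 codes grade 2 or higher events of any attribution "during the study period through day 56 follow-up [and day 84"; the bracket goes on to limit day 84 to patients in the open-label extension. Section 11.0 gives the same continuous window: such events "will be reported from initial application of topical intervention through the 56 day (and in those patients with a day 84) follow-up visit".

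**Table.** The next sentence of item 6 covers all events, treatment-emergent events, serious events and events leading to discontinuation. For these, "frequency distributions by system organ class and preferred term will be calculated and presented for each patient and each treatment side, when applicable". Item 6 also promises individual presentation and descriptive summaries.

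**Treatment after day 28.** Table 1 in section 10.0 ends blinded treatment at the day-28 visit. Under section 4.2, for a patient who continues, "pharmacy will dispense open label ruxolitinib for the patient to apply to both sides of the body"; sections 5.2 and 9.0 agree, for a further 28 days. A patient who does not continue applies neither study cream up to the day-56 visit.

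Sections 11.0, 14.0 and 16.0 do not separate the two periods, say what a treatment side means after day 28, or define treatment-emergent by period.

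**The concern.** The title announces a "Vehicle- and Comparator-Controlled Trial on Safety and Efficacy of a Topical Inhibitor of Janus Kinase 1/2", and safety and tolerability is a stated objective. The by-side table is the only planned comparison of clinician-graded adverse events between the ruxolitinib and vehicle sides. It matters because the expected local events in section 11.0, such as erythema and pruritus, are also features of the disease (table in section 3.0). The concurrent vehicle side helps to tell drug from disease and from the cream base.

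That contrast exists only up to day 28, and item 6 does not say how later events are assigned to a side. There are two natural ways, and each misleads:

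- **By randomised side.** A ruxolitinib reaction on the former vehicle side is entered as a vehicle-side event. The columns move together in relative terms, towards the finding that section 11.0 cites from earlier studies, where cutaneous events "were seen with similar frequency in vehicle and topical ruxolitinib cream groups".
- **By cream in use.** The ruxolitinib column collects more exposure than the vehicle column. The columns move apart even if the drug does nothing.

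**Working it through.** The plan gives no figure on this point, so there is none to reproduce. Step 1 follows from the plan alone. Steps 2 to 5 use assumed rates.

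**1. Exposure.** Drug is compared with vehicle on 28/56 = 50% of the window in a patient who stops and on 28/84 = 33% in an open-label patient. In an open-label patient the sides differ by 56 versus 28 ruxolitinib days, not by 28 versus 0.

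**2. Counting by randomised side.** Let *a* be the local-event rate per side per 28 days on ruxolitinib, *b* the rate on vehicle or off cream, and *c* the share who continue. All three are assumptions. Section 9.0 restricts continuation to responders while sections 4.2 and 15.2 offer it to all, so *c* is varied from 25% to 100%.

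- Open-label patient, three periods: *a + a + b* on the drug side, *b + a + b* on the vehicle side.
- Patient who stops, two periods: *a + b* versus *b + b*.
- Average per patient: drug side *a(1 + c) + b*; vehicle side *ca + 2b*; difference *a − b*.

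For example, with *a* = 0.15, *b* = 0.05, *c* = 0.5 and 24 patients: drug side 24 × (0.225 + 0.05) = 6.6; vehicle side 24 × (0.075 + 0.10) = 4.2; ratio 1.57.

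| | 15% v 5%: events | ratio | 10% v 5%: events | ratio |
|---|---|---|---|---|
| Blinded period only | 3.6 v 1.2 | 3.0 | 2.4 v 1.2 | 2.0 |
| Full window, c = 25% | 5.7 v 3.3 | 1.73 | 4.2 v 3.0 | 1.40 |
| c = 50% | 6.6 v 4.2 | 1.57 | 4.8 v 3.6 | 1.33 |
| c = 75% | 7.5 v 5.1 | 1.47 | 5.4 v 4.2 | 1.29 |
| c = 100% | 8.4 v 6.0 | 1.40 | 6.0 v 4.8 | 1.25 |

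The expected difference in counts stays at 2.4 (or 1.2) in every row. If events are independent, only the relative contrast is diluted.

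**3. Patients counted once, no events off cream.** With 28-day risks of 20% and 5% (assumed) and half continuing, the drug side shows 0.5 × (1 − 0.8²) + 0.5 × 0.20 = 28.0%. The vehicle side shows 0.5 × (1 − 0.95 × 0.8) + 0.5 × 0.05 = 14.5%. The ratio falls from 4.0 to 1.93 and the difference from 15 to 13.5 points. If all continue, the figures are 36% v 24%, a ratio of 1.5 and a difference of 12 points. The rates differ from step 2, so this supports the direction and not any particular number.

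**4. Reaction as a patient trait.** If the same 10% of patients react wherever the drug is applied, and reactors continue as often as others, the excess of patients with a drug-side event is 24 × 0.10 × (1 − c). That is 2.4 with a cut at day 28, and 1.8, 1.2, 0.6 or 0 without one, for c = 25%, 50%, 75% or 100%.

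**5. Counting by cream in use.** On-cream side-periods per patient are 1 + 2c for ruxolitinib and 1 for vehicle. With equal true rates the raw count ratio is 1 + 2c, that is 1.5, 2.0, 2.5 or 3.0 for the same four shares.

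**The case against.** The strongest reply is that this is an unfinished table shell in a descriptive pilot. The day 56/84 window stands in the coding sentence, and the tabulation sentence names no window. The phrase about applicability leaves the analyst room. With 24 patients and dated events, an individual listing would show what happened before and after day 28. The plan promises frequencies, not a ratio, and the expected count difference does not move under independence.

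Much of this stands, and it keeps the point small. It does not remove it. The coding window is the only one given, and the applicability phrase reads most naturally as covering systemic events that have no side. A listing does not correct a summary table, and a count by cream in use distorts the difference as well.

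Three stronger readings may tempt a reader, and the documents do not support them.

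- *This is the trial's only vehicle-controlled safety comparison.* Section 14.0, item 4 compares the sides on PRO-CTCAE with a paired Wilcoxon test, and section 12.0 sets this at days 14 and 28. That is a vehicle-controlled comparison of symptoms within the blinded period.
- *Reports after day 28 are biased by unblinding.* Section 4.2 says that the investigator, coordinator and patient "will become unblinded during the open label portion", but the same sentence keeps them blinded to the initial arm, and section 15.2 keeps patients blinded to arm at the end of the day-28 visit. Whether the original side is revealed is unclear.
- *The side contrast will vanish.* That needs every reactor to continue. Item 6 lists no dose change for grade 1 or 2, but it also says that treatment-related events should lead to reduced or stopped exposure. Section 13.0 removes patients whose event requires discontinuation. Reactors may well continue less often, and dilution would then be smaller.

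**Conclusion.** The point holds as a minor one. Followed as written, item 6 mixes blinded, open-label and off-cream events in a side comparison that is vehicle-controlled only to day 28, and neither reading of side repairs it.

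The firm figures are the exposure shares, 50% and 33% of the window. The rest is illustration. By randomised side, a true ratio of 3.0 reads 1.73 to 1.40 and one of 2.0 reads 1.40 to 1.25, with the expected count difference unchanged if events are independent. By cream in use, equal rates can look up to threefold different. These results rest on the assumed event rates, on an off-cream rate equal to that of vehicle (zero in step 3), and on the share who continue.

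A reader might infer that efficacy is contaminated too. It is not: the side comparisons of BSA, PGA and CAILS are set at days 14 and 28.

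**What to change.** In section 14.0, item 6:

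1. Limit the by-side adverse-event table to events with onset from first application to the day-28 visit, ruxolitinib side versus vehicle side, in all treated patients.
2. Tabulate events with later onset separately by drug status at onset (stopped at day 28, open-label on both sides, treatment extension), with no drug-versus-vehicle column.

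The cost is two or three sentences, and one table becomes two. Section 16.0 already provides that adverse events "will be recorded individually according to toxicity date", so no new data, visits or patients are needed. There are two drawbacks: the blinded-period table will hold few events and remains descriptive, and a late effect of blinded treatment that starts just after day 28 falls in the second table.
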